The Immediate, Intermediate, and Long-Term Effects of Osteopathic Manipulative
Treatment on Pulmonary Function in Adults with Asthma

IRB Approval Date: January 8, 2019

Objective

To examine the immediate, intermediate and long-term effects of OMT on the objective pulmonary function of adults with a diagnosis of asthma, as well as the subjective long-term effects.

Design

The study design for the present study was approved by the institutional review board at Des Moines University in Des Moines, IA. Written informed consent was obtained from all participants. Participants were recruited by email, class announcements, and word of mouth targeting Des Moines University (DMU) students and faculty. Inclusion criteria for participation in the study included being 18 years of age or older and having a diagnosis of asthma, regardless of whether spirometry was used in the diagnosis. Exclusion criteria included being a current smoker, having any other respiratory disease besides asthma, and receiving Osteopathic Manipulative Medicine (OMM) from a licensed physician or chiropractic or massage treatment for 30 days prior to and during the study.

Methods

Timeline

The study was conducted over a period of eight weeks. During week 0, participants completed a form regarding their age, sex, height, ethnicity, exercise habits, and current asthma medications. They completed the initial AQLQ and performed baseline spirometry testing.

During weeks 1, 2, and 3 of the study, a standard OMT protocol, detailed below, was performed on each participant, followed by spirometry testing to measure the immediate effect. Spirometry testing was then performed again three days later to measure the intermediate effect of OMT.

During week 7, participants completed the post-OMT AQLQ and performed spirometry testing once more to measure the long-term effect of OMT.

Asthma Quality of Life Questionnaire

Participants completed the Asthma Quality of Life Questionnaire with Standardized Activities (AQLQ(S)) to subjectively measure asthma severity. The AQLQ is a 32-item survey which asks participants to recall their experiences during the previous two weeks as they relate to four domains (symptoms, activity limitations, emotional function, and environmental stimuli). Each item is rated on a 7-point Likert scale, with 1 being severely impaired and 7 being not impaired at all. This was taken in week 0 to establish a subjective baseline value as perceived by the participant. Participants completed this questionnaire again in week 7 to be used as a subjective measurement of their asthma severity after OMT. We compared the mean scores for each item, each domain, and the overall average.

Pulmonary Function Measurements

Pulmonary function testing was done using a portable spirometer (McKesson LUMEON, Andover, MA, USA). Testing was conducted by one member of the research team, after training with a licensed pulmonologist. Subjects were required to perform three trials deemed acceptable by the spirometry software (Easy on-PC), and the trial with the best overall effort as determined by the highest FVC was used for analysis. The spirometric measures used to assess participants' pulmonary function included forced expiratory volume in one second (FEV1), forced vital capacity (FVC), the FEV1/FVC ratio, and peak expiratory flow (PEF).

OMT Protocol

An OMT protocol was derived from a survey of the DMU OMM Department faculty as well as current and past DMU OMM Fellows. The survey included questions regarding the approach each participant would use when treating an asthmatic patient with OMT. Based on the survey results, the current undergraduate OMM Fellows of DMU developed the standardized OMT protocol used during each of the three OMT sessions. These sessions lasted 21.3 ± 3.6 minutes. The protocol included the following techniques: supine OA joint balanced ligamentous tension (BLT), supine cervical spine Still technique, supine thoracic inlet MFR, stimulatory supine rib raising soft tissue, supine respiratory rib BLT, supine abdominal diaphragm MFR, seated thoracic spine Still technique, and seated posterior rib Still technique.

After the undergraduate OMM Fellows ([name]) completed the treatment protocol, all participants were rechecked for somatic dysfunction resolution by one of 2 board-certified OMM/MMM physicians ([name]). If inadequate resolution at a specific body region was found, that region was retreated using the same technique included in the protocol. The retreatment lasted, on average, 6.3 minutes. The final step before spirometry was performed involved one minute of stimulatory tapotement, or rhythmic tapping of the tissues, applied to the paraspinal region at the levels of the first through sixth thoracic vertebrae to target the lung viscerosomatic reflex area and potentially temper parasympathetic cholinergic tone to decrease contraction of airway smooth muscle.

Statistical Analysis Plan

Changes in FEV1, FVC, the FEV1/FVC ratio, and PEF were determined by calculating the arithmetic mean for all participants at each time point. The immediate effect of OMT was determined by comparing the measurements taken immediately after the first treatment to baseline, and the previous week's measurements to those taken immediately after the subsequent treatment. The intermediate effect was determined by comparing the measurements three days after treatment to baseline as well as the previous week's three-days-post-OMT measurements. The long-term effect was determined by comparing the measurements four weeks after the final OMT session to baseline. Each comparison was analyzed using a repeated-measure ANOVA on random subjects. The Westfall method was used to adjust p-values.

Changes in participants' survey results were determined by calculating the arithmetic mean for the overall scores and for each of the four domains, then comparing the post-OMT values to the pre-OMT values. These values were analyzed using paired t-tests.

Statistical analysis was performed using IBM SPSS[®] Software, with the guidance of [name] and [name] of the Des Moines University Research and Public Health Department, respectively.

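### With every participant treated and one reading before any OMT, the SAP's contrasts show change after OMT and cannot be attributed to it

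*Combined protocol and SAP*

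**What the plan says.** **Treatment and timing (Methods, Timeline).** At week 0, "They completed the initial AQLQ and performed baseline spirometry testing". In weeks 1, 2 and 3, "a standard OMT protocol, detailed below, was performed on each participant, followed by spirometry testing to measure the immediate effect", and spirometry is repeated three days later. A last spirometry and a second AQLQ follow in week 7. No untreated or sham group, repeated baseline, familiarisation test or same-visit reading before OMT is described.

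**Spirometry contrasts (Statistical Analysis Plan).** The immediate effect is obtained by "comparing the measurements taken immediately after the first treatment to baseline", and for later sessions by comparison with the previous week's readings. The intermediate effect sets each three-day reading against baseline and against the three-day reading of the week before. The long-term effect sets week 7 against baseline. The analysis is a repeated-measures ANOVA with Westfall-adjusted p-values.

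**AQLQ.** The Objective extends to OMT's effects on participants' own ratings ("as well as the subjective long-term effects"). The questionnaire section says: "Participants completed this questionnaire again in week 7 to be used as a subjective measurement of their asthma severity after OMT". The two administrations are compared by paired t-tests.

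**The concern.** Each contrast compares two occasions in the same treated people. Anything that moves the group between those occasions enters the difference: familiarity with the forced manoeuvre, season or exposure, effort, or expectation. The plan has no series in which these influences run without OMT, and only one occasion on which OMT has not yet been given. A significant result could therefore be reported as an effect of OMT when the schedule cannot tell it from a shared shift.

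A second difficulty is internal to the SAP. The previous-week contrasts use a reference that already follows OMT. A treatment that worked equally well every week could show nothing on them, and a difference could be misread as what one session achieved.

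**Working it through.** The documents give no sample size, effect size or estimate of practice or drift, so there is no planned figure to reproduce. The check is what the occasion means can identify.

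**Inputs (Timeline, SAP).** Occasions: week 0 (W0); immediate (P1, P2, P3) and three-day (D1, D2, D3) readings; week 7 (W7). That is 1 + 3 + 3 + 1 = 8 means per measure. Contrasts:
- Against baseline, five: P1−W0, D1−W0, D2−W0, D3−W0, W7−W0.
- Against the previous week, four: two immediate (P2 and P3) and two three-day (D2−D1, D3−D2). For the immediate pair the SAP does not say whether the reference is the previous immediate or the previous three-day reading.

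**1. No shared shift.** Baseline plus seven post-OMT effects: 8 parameters, rank 8, 0 degrees of freedom left.

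**2. Add a one-off gain g after the first test.** 9 parameters, rank 8. Raise all seven effects by k and lower g by k: the eight means do not change.
- Each contrast against baseline moves by k, so none of the five is estimable.
- In each previous-week contrast k cancels, so all four remain estimable, with either immediate reference.

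**3. Add a linear drift instead.** Assume days 0, 7, 10, 14, 17, 21, 24, 49. Again 9 parameters, rank 8. Raise each effect by k × day and lower the slope by k.
- The baseline contrasts move by 7k, 10k, 17k, 24k and 49k.
- Like-for-like previous-week contrasts move by 7k; an immediate reading against the previous three-day reading moves by 4k (for example, 14 − 10).
- None of the nine is estimable. A gain that continues with each test acts in the same way.

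**4. Do equal effects at every session help?** Parameters: baseline, immediate, three-day, long-term = 4, rank 4.
- Adding the first-test gain: 5 parameters, rank 4, because the three effect indicators sum to the gain column.
- Adding drift: 5 parameters, rank 5, so it is separable, but only if effects do not build up over sessions.
- Adding drift and linear build-up b (0, 1, 2 at sessions 1, 2, 3): 6 parameters, rank 5, because day = 7×immediate + 10×three-day + 49×long-term + 7×b.

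**5. Previous-week contrasts with an equal session effect e.** D2−D1 = 0, and P2−P1 = 0 if that is the reference. If the reference is D1, with a fraction f of e left at three days and none by the next session, P2−D1 = (1−f)e: 1.0e, 0.5e and 0 for f = 0, 0.5 and 1, plus any shift between the days.

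**6. AQLQ.** Two means: baseline and change = 2 parameters, rank 2. Adding a shared shift: 3 parameters, rank 2.

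**7. What a same-visit reading before OMT would add.** 8 + 3 = 11 means. Eight day means plus three immediate changes = 11 parameters, rank 11, so between-day shifts drop out of the immediate change. Adding three three-day effects and one week-7 effect gives 15 parameters, rank 11; those four stay non-estimable.

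**8. Why p-value adjustment does not help (illustration on assumed values only).** True OMT effect zero, shared shift of d SDs of the paired difference, two-sided t-test, noncentrality d√n, n = 10, 20, 50. At level 0.05 the rejection rates are 0.09, 0.14, 0.28 for d = 0.2 and 0.29, 0.57, 0.93 for d = 0.5. At 0.05/7, a stand-in for a multiplicity adjustment, they are 0.02, 0.03, 0.09 and 0.08, 0.25, 0.76. Adjustment lowers the rates but leaves the shift in the estimate.

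**The case against.** The case on the other side has several parts.

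- **A single-arm before-after study is legitimate, and nothing is hidden.** This stands. The SAP defines each effect by a visible comparison, the Objective is exploratory, and no efficacy conclusion is drawn. The point concerns only the label and what is later inferred from it.
- **Safeguards exist.** Three acceptable trials are required, "Testing was conducted by one member of the research team" after training, and other manual treatment is excluded. These limit variation in technique, tester and co-treatment. They do not remove practice between visits or drift over the study period.
- **Not every contrast is aliased with practice.** A reader might infer that first-test practice contaminates all the SAP's effects. Step 2 shows otherwise: the four previous-week contrasts are free of a one-off gain. Their weaknesses are drift, continuing practice and the already-treated reference.
- **Week 0 is not the only reading that precedes a session.** Correct: the three-day readings after sessions 1 and 2 come before sessions 2 and 3. They are not untreated readings, so the accurate statement is that week 0 is the only reading before any OMT.
- **No bias has been shown.** Correct. A reader might also infer that the results are wrong. The documents give no size or direction for practice or drift, and the rates in step 8 rest on assumed values. Day-to-day variation that is independent between participants costs precision only.

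**Conclusion.** The concern holds in this form. The five spirometry contrasts against baseline cannot be separated from a first-test gain or from shared time shifts (9 parameters, rank 8). The four previous-week contrasts cannot be separated from drift or continuing practice, and they do not measure a session's effect. The AQLQ change cannot be separated from shared time shifts or expectation. Neither the ANOVA nor the Westfall adjustment alters this.

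The rank results in steps 1 to 3 need no assumed effect size, and they hold for any visit spacing; the days in steps 3 and 4 are assumed for illustration. Step 5 assumes equal session effects.

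The documents do not support the stronger conclusions that bias occurred, that OMT has no effect, or that the data are unusable. They support a report of change over time after OMT.

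**What to change.** **Now, with no new data.** In the SAP labels, the report and the conclusions, or in a dated note:
- call the contrasts change from baseline (or from the previous reading) after OMT;
- state that practice, shared time shifts, and expectation or effort cannot be separated from an OMT effect;
- name the reference reading for the later immediate contrasts, and do not interpret a post-OMT reading minus the previous week's post-OMT reading as the effect of a session.

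The approved Objective can stay as it is. The cost is rewording and a weaker stated conclusion.

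**Only if OMT visits remain, or in a later study.** Repeat the same spirometry just before OMT at each visit, and define the immediate change as the within-visit post-minus-pre difference. The cost is up to three extra test sets, with possible fatigue from repeated blowing. This removes between-day shifts only. Same-visit practice, effort and expectation remain, and the three-day, week-7 and AQLQ contrasts are not rescued; separating those from shared time shifts would need a concurrent untreated series. The past tense ("The study was conducted over a period of eight weeks") and an observed session duration ("These sessions lasted 21.3 ± 3.6 minutes") suggest that the visits are already complete, so this part is most likely for a later study.
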